03 JAN 2024

STATEMENT OF COMPLIANCE

This study will be carried out in accordance with Good Clinical Practice (GCP) as required by the U.S. Code of Federal Regulations applicable to clinical studies (45 CFR 46), and the International Commission on Harmonization (ICH) guidelines for Good Clinical Practice (GCP) E6. Investigators will complete and remain current with appropriate Human Subjects Protection Training. The study will be conducted in accordance with HHS-regulatory compliance for the Federal Wide Assurance and Institutional Review Boards (IRB).

SIGNATURE PAGE

The signature below constitutes the approval of this protocol and the attachments and provides the necessary assurances that this trial will be conducted according to all stipulations of the protocol, including all statements regarding confidentiality, and according to local legal and regulatory requirements and applicable US federal regulations and ICH guidelines.

The University of Rochester Institutional Review Board will be guided by the ethical principles described in the Belmont Report and by the regulations of the U.S. Food and Drug Administration (21 CFR 50 and 56) and the U.S. Department of Health and Human Services (45 CFR 46). The University of Rochester maintains an Assurance of Compliance with the Office for Human Research Protection (OHRP).

Primary Investigator: [name].

Signed:

Date:

[name]
Professor of Medicine

Title: An Assessment of immunogenicity of licensed Respiratory Syncytial Virus (RSV) vaccines in residents of Long-Term Care Facilities (LTCF) and community-dwelling older adults planning to receive RSV vaccination as part of medical care.

Population: Adults \geq 60 years of age: 76 residents of LTCF and 76 participants from community-dwelling adults. Adults living in the community will serve as the control group to reflect the study population enrolled in the Phase 3 Trials of the Pfizer and GSK RSV vaccines.

Number of Sites: The study will be conducted at 3 sites (URMC and 2 local LTCF).

Study Duration: 6 months

Participant Duration: The protocol requires a participant to remain in the study for 1 month.

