Objectives: The primary objective of this study is to compare the neutralizing antibody response at one-month post-vaccination with a licensed RSV vaccine in adults \geq 60 years of age living in skilled nursing facilities with adults living in the community. A secondary objective will be to evaluate the binding antibody responses to RSV preF proteins at 1 month.

Study Design

The study will be conducted at URMC and 2 local LTCFs. Approximately 76 persons \geq 60 years of age who live in LTCF and an equal number of older adults living independently in the community who are planning to receive one of the licensed RSV vaccines as part of standard of care (SOC) will be recruited for participation in the study.

Study procedures: Visits will occur at the LTCF for residents of LTCF or in the research clinic for community-dwelling older adults. After informed consent by the participant or legally authorized representative (LAR), demographic and medical history will be collected and a symptom-targeted physical exam will be performed. A 10 cc blood sample will be collected prior to vaccination. Following vaccine administration, individuals will be monitored for 15 minutes for immediate adverse events. One additional visit will occur at 1 month post vaccination at which time 10 cc of blood will be collected, the participant will be interviewed and medical records reviewed. Subjects will be queried about any intervening respiratory illnesses and persons testing positive for RSV infection as part of the standard of care (SOC) after vaccination or by a non-vaccine RSV protein by ELISA and before the 1-month blood draw will not be included in the immunogenicity analysis. Serum samples will be tested for binding (RSV A and RSV B PreFusion F, Attachment (G) protein) and neutralizing antibodies to RSV A and RSV B in the URMC research laboratory.

BACKGROUND and RATIONALE

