Study Procedures:

For residents of LTCF all procedures will be conducted on-site at the LTCF and for the community cohort, all procedures will be conducted in the research clinic. No study procedures will be performed prior to consent.

It is anticipated that most LTCF residents will have a screening/enrollment visit and that vaccination will occur separately as per the LTCF vaccination plans. In most cases, the community cohort will have screening and vaccination on the same visit.

Schedules of Activities are listed below.

Schedule of Activities

| Category of Activity | Research | Standard of Care | Research |
|--|-----------------------------------|------------------|------------------------------------|
| Visit Number | V0 ^a | V1 ^a | V2 |
| Visit Type | Screening and Enrollment | Vaccination | 1-month (D28) |
| Visit Window | up to -21 days before vaccination | | D21-42 after vaccination/infection |
| Visit Location | LTCF/clinic | LTCF/clinic | LTCF/clinic |
| Informed Consent | up to -21 days before vaccination | | |
| I/E | X | | |
| Medical History | X | | X |
| Vaccine History | X | | X |
| Prohibited Medication Review | X | | X |
| Vital Signs | X | X ^c | |
| Targeted PE ^b | X | X ^c | |
| Collect 10cc serum | X | | X |
| Vaccinate | | X | |
| 15-minute Observation (post vaccination) | | X ^c | |
| Review ARI history and test results | | | X |
| SAE review | | | X |

^a Informed consent and screening activities can be separate or combined with Visit 1.

^b Targeted physical exam will be performed on screening and before vaccination only as clinically indicated based on the presence of signs or symptoms warranting further investigation.

^c Vaccination related procedures will be guided by SOC at each location

CONSENT PROCESS

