- Obtain and record the participant's demography (including complete date of birth, sex, race, racial designation, and ethnicity)
- Obtain and record medical history
- Obtain and record details of any non-study vaccinations, and prohibited concomitant medications and treatments
- Perform a clinical assessment including vital signs (Blood pressure, heart rate and oxygen saturation) and symptom-targeted physical exam
**Note: Height and weight will be recorded as by participant report or medical record in LTCF.*
- Collect 10 cc of serum
- Confirm contact and alternate contact information with participant and LTCF staff
- Schedule visit 2.

Visit 1 (Standard of Care) [Vaccination: For LTCF this will be performed by LTCF staff per their facility protocol and for Community Cohort this will be performed in the clinic]

- Perform a clinical assessment including vital signs (Blood pressure, heart rate and temperature) and symptom-targeted physical exam as dictated by location of vaccination standard procedures.
- Vaccinate with ABRYSVO or AREXVY and in non-dominant arm and document product, time and location.
- 15 minutes of observation in the clinic, in LTCF standard practice will be followed

If a person has an intercurrent RSV infection and is not vaccinated as part of SOC, visit 2 will be scheduled 28-42 days after infection was documented.

Visit 2 (Research Procedures) [1-month]

- Verbally confirm the participant wishes to continue in the study
- Obtain and record any new medical history
- Inquire about any respiratory illnesses and record results any viral testing performed.
- Collect information on AEs, SAEs related to study procedures
- Obtain and record details of any non-study vaccinations, and prohibited concomitant medications and treatments
- Perform a symptom-targeted clinical assessment and physical exam
- Collect 10 cc of serum.

Individuals who do not meet the criteria for participation in the study (screen failure) can be rescreened if the exclusionary condition is considered to be temporary in nature by the investigator.

Only the following information will be collected on screen failures: demographics (age, screen number, sex, ethnicity, and race) and reason for ineligibility. Participants who are found to be ineligible will be told the reason for ineligibility.

LABORATORY METHODS:

RSV PCR will be performed as standard of care in the LTCF.

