Enzyme Immunoassay (EIA): Serum IgG titers to RSV F (prefusion) protein of group A and B RSV will be determined by enzyme immunoassay using established methods.²⁸ Briefly, purified RSV proteins are coated to 96-well EIA plates to which serum 2-fold dilutions are added in duplicate. Bound antibody is detected with alkaline phosphatase-conjugated goat anti-human IgG antibody and substrate.

Microneutralization Assay (MNA): Serum neutralizing titers will be performed using an established microneutralization method for RSV A and B strains.²⁸ Briefly, 2-fold serum dilutions are incubated with 75 plaque forming units of RSV for 30 min at room temperature followed by the addition of 10⁴ HEp-2cells in 96-well culture plates. After 3 days, the quantity of RSV antigen is determined by enzyme immunoassay using a monoclonal antibody to the RSV F protein. The neutralization titer is defined as the serum dilution that results in a 50% reduction in color development.

ANALYTICAL AND STATISTICAL METHODS

The primary immunogenicity analysis will include persons vaccinated but without documented RSV infection (PCR or G ELISA). The immune response to infection alone or combined infection and vaccination will be analyzed descriptively and separate from the primary analysis. This study is designed to demonstrate non-inferiority to within a 1.5-fold difference in the 1-month titer level, adjusting for baseline titer level. Since the distribution of titer levels is strongly positively skewed, and we are interested in relative changes, all titer levels

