Based on data from 52 participants in a prior study of the Pfizer RSV vaccine, the geometric mean titer level was estimated to be 2218 (95% CI: 1822-2699) at baseline, and 22,510 (17,003-29,799) at 1-month, corresponding with a relative change of 10.15-fold (95% CI: 7.39-13.95). From this data we estimate the Standard Deviation (SD) of log(titer) to be 0.71 at baseline and 1.01 at 1-month, while the SD of the 1-month change in log(titer) is 1.14 –larger than SD (log (1-month titer)), indicating that a 2-sample t-test of the change in log(titer) would be less efficient than a t-test of the 1-month log(titer). Since we plan to adjust for baseline log(titer), our residual SD $< \min(\text{SD}(\log(1\text{-month titer})), \text{SD}(\log(\text{relative change in titer}))) = \min(1.01, 1.14) = 1.01$. But not much less, since the prior data suggests the correlation between baseline and 1-month log(titer) is very weak ($r=0.14$), with log (baseline titer) explaining only 2% of the variability in log (1-month titer). In particular, we estimate residual SD = 1, suggesting that a 2-sample t-test of log (1-month titer) would be nearly as efficient as our linear model-based test adjusting for log (baseline titer). Given this estimate of variability (SD=1), a sample size of 76, 89, or 105 per group provides 80%, 85%, or 90% power to demonstrate non-inferiority to within a relative non-inferiority margin of 1.5-fold using a 1-sided 0.05 level linear model-based t-test comparing log (1-month titer) by population, adjusted for log (baseline titer). We have chosen a sample size of 76 in each group which will provide 80% power to demonstrate non-inferiority.

POTENTIAL RISKS AND BENEFITS

This study may be associated with risk due to sample collection or loss of privacy.

Sample Collection:

- **Blood draws:** A blood draw may cause faintness, inflammation of the vein, pain, bruising, or bleeding at the site of the puncture. There is also a slight chance of infection.

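### The 80% power figure needs 76 analysed per group, but about 76 per group is also the number to be recruited, with no allowance for people the primary analysis leaves out.

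*Combined protocol and SAP*

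**What the plan says.** Power and Sample Size Considerations states that "a sample size of 76, 89, or 105 per group provides 80%, 85%, or 90% power" for a one-sided 0.05 test of log 1-month titer by population, adjusted for log baseline titer. It ends: "We have chosen a sample size of 76 in each group which will provide 80% power to demonstrate non-inferiority".

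The same number is the enrolment target. The Population entry of the synopsis gives "76 residents of LTCF and 76 participants from community-dwelling adults". The Study Design entry says that approximately 76 LTCF residents, and an equal number from the community, who plan to be vaccinated "as part of standard of care (SOC) will be recruited for participation in the study".

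The plan also describes how enrolled people can fall outside the primary comparison:

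- **Analytical and Statistical Methods:** "The primary immunogenicity analysis will include persons vaccinated but without documented RSV infection (PCR or G ELISA"). Infected people are analysed descriptively and separately.
- **Synopsis, Study procedures:** people found to be infected after vaccination and "before the 1-month blood draw will not be included in the immunogenicity analysis".
- **Study Procedures:** "most LTCF residents will have a screening/enrollment visit and that vaccination will occur separately". The Schedule of Activities allows up to 21 days between enrolment and vaccination.
- **Visit 1:** "If a person has an intercurrent RSV infection and is not vaccinated as part of SOC, visit 2 will be scheduled". Such a person stays in follow-up without having been vaccinated.
- **Consent Process and Participant Status:** withdrawal is allowed at any time, including when a representative has consented but the participant does not wish to take part.

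**The concern.** A power figure for a model-based test refers to the people who enter the model. Here that means vaccinated participants, without documented infection, who have both titers. If 76 is the number needed in the model and about 76 is the number enrolled, each unvaccinated, infected, withdrawn or unsampled participant lowers power below the stated value.

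Such losses are likelier in the LTCF group, where enrolment usually precedes vaccination, than in the community group, which is mostly screened and vaccinated at one visit.

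What is at stake is how a failure to show non-inferiority would be read. Readers would judge the adequacy of the study by an unconditional 80% that the design does not secure. The non-inferiority rule and its type I error are unaffected.

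**Working it through.** **Inputs.** From Analytical and Statistical Methods and Power and Sample Size Considerations:

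- Margin 1.5-fold, so ln 1.5 = 0.4055.
- One-sided alpha 0.05.
- Residual SD 1, from 1.01 × √(1 − 0.14²) = 1.000.
- True ratio 1. The plan does not state this, but its sample sizes imply it.

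**Formula.** SE = SD × √(1/n₁ + 1/n₂). Non-centrality = 0.4055 / SE. Degrees of freedom = n₁ + n₂ − 3 (intercept, population, baseline titer). Power is the probability that a non-central t with these values exceeds the one-sided 5% critical value of t.

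**Reproducing the plan.** At 76 v 76: SE = √(2/76) = 0.1622, non-centrality = 0.4055/0.1622 = 2.50, df = 149, power 80.04%. At 89 per group it is 85.3% and at 105 it is 90.0%. All three stated figures are confirmed.

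**Reserve.** There is none. At 75 v 75 power is 79.6%. It stops rounding to 80% at three LTCF losses (73 v 76, 79.3%) or two losses per group (74 v 74, 79.1%).

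**Power if 76 per group are recruited and some are lost.** The documents give no loss rate, so every rate below is an assumption. The evaluable number is 76 × (1 − loss), rounded down: 72 at 5% and 68 at 10%.

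| Assumed loss | Analysed (LTCF v community) | Power |
|---|---|---|
| None | 76 v 76 | 80.0% |
| LTCF 5% | 72 v 76 | 79.1% |
| LTCF 10% | 68 v 76 | 78.0% |
| LTCF 10%, community 5% | 68 v 72 | 77.1% |
| Both 5% | 72 v 72 | 78.1% |
| Both 10% | 68 v 68 | 76.0% |

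The chance of missing true non-inferiority thus rises from 20% to about 21–22% (LTCF loss only) or 22–24% (both groups).

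The Background gives LTCF infection rates of 1–12%. It states no period for them, so they cannot serve as a one-month loss rate.

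**Scale against the SD.** The SD comes from 52 people. An approximate 95% interval is 1 × √(51/χ²) on 51 df, or 0.84 to 1.24. At 76 v 76 those limits give power of 91% and 64%.

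**Search for an allowance.** No section gives an inflation factor, a replacement rule or a definition of 76 as evaluable. The provisions on temporary delay and rescreening deal with ineligibility and screen failure. They narrow the loss, but do not cover infection after enrolment, later withdrawal or a missing serum.

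**The case against.** The strongest reply is that the effect is small and the loss rates are assumed. A residual SD of 0.97 instead of 1 would offset a 5% loss in both groups (72 v 72: 80.3%), so a rounded planning SD cannot really separate 78% from 80%. The implied true ratio matters more: at a ratio of 0.95, power at 76 v 76 is 70.1%.

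Several features also point to low loss. There is a single follow-up visit at about one month with a 21–42 day window. LTCF visits are on site. Participants must have a life expectancy over six months and must already plan to be vaccinated, and they are paid per visit. Community participants are mostly vaccinated at the enrolment visit, so the scenario with 10% loss in both groups is the least supported. Finally, the synopsis says approximately 76, which leaves some room to recruit more.

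Most of this stands as a limit on size. It does not answer the point. Low loss is not zero loss, and three LTCF losses are enough to move the rounded figure. Approximately is not an allowance. The SD could err in either direction, whereas loss from a fixed enrolment can only reduce the number analysed. On the plan's own chosen SD, 80% needs 76 analysed per group.

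**Conclusion.** The concern holds. The sample size is computed correctly, but the plan uses one number both as the analysed sample that gives 80% power and as the approximate enrolment, while itself providing for enrolled people who cannot enter the primary analysis. The unconditional 80% is delivered only if almost nobody is lost.

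The likely cost is about 1–4 percentage points of power, on the assumptions of 5–10% loss, SD 1 and a true ratio of 1. That the allowance is missing is certain; the size of the effect depends on a loss rate the documents do not give. Nor is 80% a strict ceiling: at SD 0.95, 72 v 72 gives 81.7%. This should be corrected because the stated property is not secured and the correction is cheap, not because the study is badly undersized.

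**What to change.** In Power and Sample Size Considerations, replace the last sentence with:

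> The 80% power applies to 76 evaluable participants per group (residual SD 1, true ratio 1). With approximately 76 recruited per group and an expected non-evaluable fraction of [investigators' estimate]% in LTCF and [investigators' estimate]% in the community, power is about [value]%.

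The value can be taken from the table above: about 78–79% for 5–10% loss in LTCF only, and about 76–78% for 5–10% loss in both groups. The blanks have to be filled by the investigators because the documents give no loss rate.

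The cost is a two-sentence edit, with no change to enrolment, conduct or analysis. The stated power falls by about 1–4 points, and the investigators must commit to a loss estimate for each group.

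No increase in enrolment is asked for. If the team would rather keep 80%, the recruitment needed per group is 76/(1 − loss): 76/0.95 = 80 at 5% and 76/0.90 = 84.4, so 85, at 10%. That is 160 or 170 in total instead of 152.
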